et.al(($\sigma=10$) and Type I (α) error 0.05 and power 80% to achieve 12 score difference in mean of GMFC after intervention. The minimum number of patients required for this study was estimated 108 subjects, which are in each of the three groups MNC, MSC and Control 36 patient allocated, respectively.

Number of subjects N in each of two groups (Diggle *et al.*, 2002)

$$N = \frac{2(z_{\alpha} + z_{\beta})^2 (1 + (n - 1)\rho)}{n[(\mu_1 - \mu_2)/\sigma]^2}$$

- σ^2 is the assumed common variance in the two groups
- $\mu_1 - \mu_2$ is the difference in means of the two groups
- n is the number of timepoints
- ρ is the assumed correlation of the repeated measures

Randomization:

The patients are randomly allocated into three groups of intervention and control using a balanced block randomization technique. To do that, they were divided into blocks of 6 and 9. All subjects randomly allocated with online randomization software to generate random-number sequences. {Sealed Envelope Ltd. 2015.

Create a blocked randomization list. [Online] Available from:

<https://www.sealedenvelope.com/simple-randomiser/v1/lists> [Accessed 15 Dec 2015]}. Coordinator and Physician responsible for assessing inclusion / exclusion criteria and registering individuals are blind.

Due to necessity of HLA matching of hematopoietic stem cells derived from allogeneic umbilical cord (MNC) group we selected 150 cases of referred patients with our inclusion criteria and HLA analysis were done for these patients and then

36 cases of class 6 matched patients enrolled to the MNC group and 72 cases among the remaining patients randomly divided to mesenchymal stem cells derived from allogeneic umbilical cord (MSC) and control group . Therefore 108 cases enrolled in 3 divided groups of 36 patients.

Statistical analysis:

Intent-to-treat approach will be used to compare the mean GMFC as the initial outcome among the three groups. One-way analysis of variance will be used to investigate the difference between mean GMFC according to the study variables. Then, the post-hoc Scheffe test is used to determine the means differences. Moreover, backward stepwise multivariate linear regression will be used to evaluate the relationship between variables. The GEE model is used to evaluate the outcome changes over time. All analyses were performed at a significance level of 0.05 using the Stata 11 (StataCorp, College Station, TX, USA) statistical software.

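### The backward stepwise regression selects terms on their p-values and does not protect the three-level arm factor; a regression with terms fixed in advance is better and costs almost nothing

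*Combined protocol and SAP*

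**What the plan says.** The Statistical analysis section of the combined protocol and SAP sets out four steps.

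- The between-arm comparison: "Intent-to-treat approach will be used to compare the mean GMFC as the initial outcome among the three groups".
- The test for it: "One-way analysis of variance will be used to investigate the difference between mean GMFC according to the study variables", after which "the post-hoc Scheffe test is used to determine the means differences".
- An additional regression: "backward stepwise multivariate linear regression will be used to evaluate the relationship between variables".
- A GEE model for change over time.

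One sentence covers all of them: "All analyses were performed at a significance level of 0.05".

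For the regression, the plan does not name the outcome, the candidate variables, the removal threshold or any term that must stay in. It does not say whether arm is a candidate or, if it is, whether it enters as one factor or as two indicators. Nor does it call the regression exploratory.

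**The concern.** Backward elimination uses the data to choose the model. The surviving terms are then read at 0.05 as if the model had been fixed beforehand. The printed p-values and intervals ignore that choice, so they do not have their nominal properties.

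Arm adds a specific risk. It has three levels, so a regression codes it as two indicators with control as reference. If software may remove these one at a time, removing one places that arm in the reference group. The surviving coefficient then compares one product with a mixture of control and the other product, whereas the Objectives section asks for comparison with control. Nothing in the output would flag the change.

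At stake is a reported arm effect that is diluted, has too narrow an interval, and sits beside the Scheffé result with no statement of which one governs.

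**Working it through.** **Inputs from the documents.** Three arms of 36 ("Therefore 108 cases enrolled in 3 divided groups of 36 patients"). SD 10, with "Type I (α) error 0.05 and power 80% to achieve 12 score difference in mean of GMFC after intervention" (Sample size calculation). Level 0.05, taken as two-sided.

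**Assumptions, because the plan is silent.** Arm is a candidate, coded as two separately removable indicators. Removal is at p≥0.05. There are 8 independent covariates with no effect. Errors are normal with equal variance, there is no dropout, and the arms are comparable apart from any true effect.

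**The plan's own figure.** The plan states no error rate or coverage for this regression, so there is none to reproduce. Its 36 per arm is taken as given. (With one timepoint its formula gives 2(1.96+0.84)²/(12/10)² = 10.9, that is 11 per group. That gap is a separate matter.)

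**Step 1: how often one arm is dropped.** The standard error of an arm-versus-control difference is 10√(2/36) = 2.357. The full model has 108−1−2−8 = 97 residual df, so the critical value is 1.985. The chance that an arm with true effect d is not significant is approximately Φ(1.985 − d/2.357):

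- d = 6: Φ(1.985−2.546) = Φ(−0.56) = 0.29
- d = 4: Φ(1.985−1.697) = Φ(0.29) = 0.61
- d = 12: Φ(1.985−5.091) = Φ(−3.11) = 0.001
- d = 0: 0.95

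**Step 2: what the surviving coefficient estimates.** With equal arms and the second arm pooled into control, it estimates d₁ − d₂/2. Effects 12 and 6 give 12−3 = 9; 12 and 4 give 12−2 = 10; 12 and 0 give 12.

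**Step 3: coverage in the pooled trials.** The standard error becomes 10√(1/36+1/72) = 2.04 and the half-width about 1.985×2.04 = 4.05. The true value of 12 is covered when the estimate exceeds 7.95. Centred on 9, that has probability 1−Φ((7.95−9)/2.04) = 0.70; centred on 10, 1−Φ((7.95−10)/2.04) = 0.84. The simulated figures in Step 4 are higher for 12 and 6 because they average over all retained arm intervals, including trials in which both terms stay.

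**Step 4: simulation of the whole elimination** (least significant term removed until all p<0.05; several thousand replicates per scenario).

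| True effects | Exactly one arm term kept | Mean effect then reported | Coverage, retained arm intervals | Coverage, full model |
|---|---|---|---|---|
| 12 and 6 | about 28% | 9.0 | about 92% | about 95% |
| 12 and 4 | about 60% | 10.0 | about 89% | about 95% |
| 12 and 12 | 0.2% | – | about 95% | about 95% |
| 12 and 0 | 95% | 12.0 | – | about 95% |

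**Step 5: false positives with no true effect.**

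- Any arm term significant after elimination: 9.7% with no covariates, 10.3% with 5, 10.6% with 10.
- The same two indicators with no selection: 9.0% to 9.2%.
- Each arm separately: 5.3% to 5.9% with selection, 5.0% without.
- Arm kept or dropped as one 2-df term: 5.1% to 5.7%.
- One-way ANOVA F test: 5.0%.

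Selection therefore adds about one percentage point. The rest of the rise above 5% comes from two unadjusted tests against control. Selection does more harm in one mixed case without covariates: if one arm has a true effect of 0.5 SD and the other none, the null arm is declared significant in 8.6% of trials, against 5.0% without selection, because the wrong indicator is sometimes removed.

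**Step 6: null covariates.** At least one survives in about 23%, 34% and 48% of trials with 5, 8 and 12 candidates. Independent tests without selection would give 1−0.95^k = 23%, 34% and 46%. This is almost entirely ordinary multiplicity.

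**The case against.** The strongest reply is that the plan assigns the arm comparison to ANOVA with Scheffé tests and adds the regression afterwards, without naming any treatment contrast. That stands: the regression changes no ANOVA, Scheffé or GEE result. A reader who infers that the trial's main comparison is invalid goes further than the documents allow.

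Second, a reader might infer that stepwise selection doubles the false-positive rate for an arm effect, since about 10% is twice 5%. The documents and the arithmetic do not support this. Two unadjusted tests against control already give about 9%, and the plan's Scheffé step deals with that multiplicity for its own comparison.

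Third, a reader might infer that the plan's rule pools an arm with control. No such rule is written. The pooling needs arm to be a candidate, coded as separable indicators. As a single 2-df term it cannot be split. What the documents show is an omission that permits the harmful version.

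Fourth, the dilution depends on the effects assumed. It needs a second arm with a real but smaller effect. It is negligible at 12 and 12, and at 12 and 0 the mean estimate is not diluted. This also stands.

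The reply does not remove the general defect. Whatever the candidates, results from a selected model are to be read at 0.05 with no exploratory label, and nothing excludes arm from that model.

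**Conclusion.** The concern holds in a limited form. Inference at 0.05 after backward elimination is not valid as stated, and the plan leaves the arm factor unprotected. If arm enters as two removable indicators with removal at p≥0.05, one arm term alone survives in about 28% of trials at true effects 12 and 6, and in about 60% at 12 and 4. The reported effect then averages 9.0 or 10.0 instead of 12, and coverage of retained arm intervals is about 92% or 89% instead of about 95%.

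These sizes rest on the assumed coding, threshold, 8 covariates and true effects, and on normal, equal-variance data without dropout. They also assume comparable arms, which the filling of the MNC group by HLA match may upset; that is a separate question.

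The point concerns a supplementary analysis. It is worth acting on because a better method is available at almost no cost, not because the main comparison is at risk.

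**What to change.** In the Statistical analysis section, replace the backward elimination with wording to this effect:

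- One linear regression is fitted, with its outcome and all its terms listed before unblinding. No term is removed on its p-value.
- Arm is always included as a single factor with control as reference and is tested jointly on 2 df. Pairwise contrasts are adjusted for multiplicity, for example by the Scheffé method already in the plan.
- Any analysis of predictors is reported from the full pre-listed model and labelled exploratory.
- No conclusion about an arm is drawn from a model whose terms were selected on the data.

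The joint test and adjusted contrasts are needed. Keeping both indicators in and reading each at 0.05 would leave the any-arm false-positive rate near 9%.

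The cost is a few sentences of SAP text, a few degrees of freedom (97 residual df remain with two arm terms and 8 covariates in 108 children) and slightly wider intervals. Recruitment, visits and treatment do not change.
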